## 9 **DETAILS OF ASSESSMENTS**

Parental assistance for study drug application and study conduct procedures may be needed for younger subjects qualifying for study participation.

### 9.1 **Baseline/Day 1 Assessments**

The Baseline/Day 1 visit for this study occurs on the same day as the Week 12/study exit visit of the DRM01B-ACN03 or DRM01B-ACN04 visit. Therefore, if subjects choose to enroll in this study, study procedures will not be repeated; study sites will carry over the information from the DRM01B-ACN03 or DRM01B-ACN04 study to the Baseline/Day 1 visit for this study.

The study procedures that are to be carried over are:

- Demographic information: age, gender, race, ethnicity and Fitzpatrick Skin Type
- Medical history
- Adverse events
- Local skin reactions
- Concomitant medications
- Laboratory evaluations: hematology, serum chemistries and urinalysis
- Pregnancy testing
- 12-lead ECG
- Investigator Global Assessment of acne

- Photography (at selected sites)
- Vital signs and weight
- Acne Patient Self-Questionnaire

## 9.2 Acne Patient Self-Questionnaire

Subjects will be asked to complete Acne Patient Self-Questionnaire. The questionnaire is paper-based and will be completed by subjects during clinic visits (see [Appendix 2](#)). Subject responses will be entered in the eCRF by the study site and the completed questionnaires kept as part of the subject’s source document. Study site staff must review all forms to ensure complete responses prior to a subject leaving the study site.

## 9.3 Assessment of Efficacy

### 9.3.1 Investigator Global Assessment

An Investigator Global Assessment (IGA) of acne severity on the face only will be conducted for each subject every 12 weeks (Table 1).

Where possible, **the same efficacy assessor should assess acne severity on the same subject at all visits**. At the Week 12 and 24 visit, if the severity of acne has become worse, as determined by the IGA, the investigator should assess whether or not the subject should be withdrawn from the study. If the decision is made to withdraw the subject, all Early Termination Visit procedures should be completed. For additional details regarding subject withdrawal, please refer to [Section 10.2](#) Early Study Termination of Study Subjects.

Individuals performing the IGA will be trained and certified prior to study start. IGA grades will be entered into the eCRF.

**Table 1: Investigator Global Assessment**

Investigator Global Assessment	
Grade	Description
0	Clear; normal, clear skin with no evidence of acne vulgaris
1	Almost clear; Rare non-inflammatory lesions present, with rare non-inflamed papules (papules must be resolving and may be hyperpigmented, though not pink-red)
2	Mild; some non-inflammatory lesions are present, with few inflammatory lesions (papules/pustules only; no nodulocystic lesions)
3	Moderate; non-inflammatory lesions predominate, with multiple inflammatory lesions evident: several to many comedones and papules/pustules, and there may or may not be one small nodulocystic lesions
4	Severe; Inflammatory lesions are more apparent, many comedones and papules/pustules, there may or may not be a few nodulocystic lesions

## **9.4 Assessment of Safety**

### **9.4.1 Physical Examination**

A complete physical examination will be conducted at Day 1 and Week 36 (End of Treatment) visit and cover general appearance, dermatological, head, ears, eyes, nose, throat, respiratory, cardiovascular, abdominal, neurological, musculoskeletal, and lymphatic body systems. A symptom directed physical exam may be performed at other clinic visits, if needed, to assess the subject. Weight will be recorded with the end of study physical exam. Findings will be recorded in the source document and eCRF.

### **9.4.2 Pulse and Blood Pressure**

Pulse (beats per minute), and blood pressure (mmHg), will be obtained with the subject in the seated position, after sitting for at least 5 minutes. Any abnormal findings which are new or worsened in severity and clinically significant, in the opinion of the Investigator, will be recorded as an AE.

Pulse and blood pressure measurements will be recorded in the source document and eCRF.

### **9.4.3 ECGs**

12-lead ECG measurements will be obtained for all subjects at the Day 1 and Week 36 Study Exit or Early Termination visits. The subject should rest quietly for at least 5 minutes in a supine position prior to ECG collection. The ECG should be obtained either prior to the time of blood collection, or at least 15 minutes afterwards.

All study sites will be supplied with standardized, validated digital 12-lead ECG (12 lead at 25 mm/sec reporting rhythm, ventricular rate, the RR interval, the PR interval, QRS duration, QT and QTcF intervals) equipment capable of recording, storing, and printing producing high resolution 12-lead ECG data by the central laboratory. Study sites will be trained on the use of the equipment prior to study start.

Machine-read ECG recordings will be collected and analyzed centrally. Data will be transferred electronically to the database.

### **9.4.4 Laboratory Evaluations**

Laboratory tests will be collected to evaluate safety in all study subjects and analyzed using a central laboratory. Labs will be collected per the Schedule of Visits and Procedures (see [Appendix 1](#)) or more frequently as clinically indicated. Laboratory samples are to be shipped on the same day as collected. No more than 4 mL/kg total will be collected over an 8-week period in subjects under legal adult age. Laboratory tests are described below.

Hematology: hematocrit, hemoglobin, red blood cell (RBC) count, white blood cell count and differential (%), mean corpuscular hemoglobin (MCH), mean corpuscular hemoglobin concentration (MCHC), mean corpuscular volume, RBC morphology, platelet count, absolute

neutrophils, absolute lymphocytes, absolute monocytes, absolute eosinophils, and absolute basophils.

Chemistry: sodium, potassium, chloride, calcium, phosphorus, bicarbonate, uric acid, blood urea nitrogen (BUN), creatinine, total protein, albumin, aspartate aminotransferase (AST), alanine aminotransferase (ALT), alkaline phosphatase, bilirubin (total and direct), and glucose (fasting or non-fasting).

Serum pregnancy testing will be performed at Baseline/Day 1 and Week 36 Study Exit or Early Termination visits. Urine pregnancy testing (beta human chorionic gonadotropin [ $\beta$ -hCG]) will be performed at Weeks 4 – 36 visits for all females unless post-menopausal/sterile.

Urinalysis: pH, specific gravity, protein, glucose, ketones, bilirubin, blood, nitrite, urobilinogen, leukocyte esterase. A microscopic examination of urine will be performed if clinically indicated (e.g. a positive dipstick for protein, blood, leukocyte esterase) in the opinion of the Investigator based on the findings of the urinalysis or clinical signs and symptoms. Any new or worsened clinically significant laboratory result is to be recorded as an AE after study drug dosing.

The central laboratory should be used for any laboratory testing required for a subject during study participation, including laboratory testing needed for unscheduled visits. If an immediate result is required to adequately care for a subject, a duplicate sample may be submitted to a local lab. Clinically significant laboratory results must be recorded as an AE, preferably as a diagnosis rather than individual test results. Any subject who has a clinically significant laboratory test result will be evaluated by the Investigator, and will be treated and/or followed up until the value returns to clinically acceptable levels, in the opinion of the investigator.

#### **9.4.5 Local Skin Reactions**

All subjects will be assessed for LSRs, on the face, at each visit. LSRs include burning/stinging, pruritus, erythema, dryness and peeling. Each LSR will be scored as 0 (None), 1 (Mild), 2 (Moderate) or 3 (Severe) (Table 2). LSRs observed on a visit day will not be recorded as adverse events unless scored as 3 (Severe). Local skin reactions experienced by the subject in between study visits are to be recorded as an AE.

Burning/stinging and pruritus will be assessed by the subject and erythema, dryness and scaling will be assessed by the Investigator/designee (Table 3). Subjects will be read the definition of each subject-assessed LSR and asked to select the appropriate definition. The corresponding grade will be assigned by the site and entered in the eCRF.

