#### **9.4.10 Dosing Changes Due to AEs**

Dose interruptions are allowed should a subject experience intolerable treatment-related adverse events (e.g., pruritis) on study. In cases where the Investigator feels a dose interruption is warranted, the subject should be instructed to interrupt study drug application to allow symptoms to resolve. Subjects should be instructed to return to the twice daily application regimen within 2 days of dose interruption.

Dosing interruptions are to be recorded in the subject diary as a missed dose.

Study drug must be discontinued if an adverse event is deemed persistent and if continuation of study drug would not be in the best interest of the subject.

Refer to [Section 10.3](#) for further information regarding discontinuation of study drug or early withdrawal.

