### **10.3 Study Drug Discontinuation**

For subjects who decide to prematurely discontinue study drug treatment, all reasonable efforts should be made to obtain all protocol-specified safety assessments and end of study procedures.

The Investigator should stop study drug treatment in the following instances:

- Inter-current illness that would, in the judgment of the Investigator, affect assessments of clinical status to a significant degree. In such cases, the Investigator must contact the Sponsor or designee, as the need to withdraw the subject will be assessed by the Sponsor
- Unacceptable toxicity

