### **6.2 Disposition of Subjects**

The number of subjects included in the safety population will be summarized for all subjects, for subjects that received Olumacostat Glasaretil Gel, 5.0% in ACN03/ACN04, and for subjects that received Olumacostat Glasaretil Gel, Vehicle in ACN03/ACN04. The number of subjects enrolled, completed, and discontinued (including the reasons for discontinuation) will be summarized similarly.

Subjects who are excluded from the safety population will be summarized by the reasons for exclusion.

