## 6.8.2 Adverse Events

AEs from ACN03/ACN04 will be included in the analysis for study ACN05. All AEs will be classified on the basis of Medical Dictionary for Regulatory Activities (MedDRA) terminology. Treatment-emergent AEs (TEAEs) are defined as AEs with an onset on or after the date of the first application of Olumacostat Glasaretil Gel, 5.0% (from ACN03/ACN04 or ACN05). If treatment-emergent status cannot be determined (e.g., unknown date of first application), the AE will be considered treatment-emergent. AEs noted prior to the first study drug administration that worsen after baseline will also be reported as AEs and included in the summaries.

TEAEs will be summarized in total as well as by 12-week periods based on time of onset in relation to date of first application of Olumacostat Glasaretil Gel, 5.0%, based on the definitions below.

- 0-12 Weeks            0 <= onset day <= 85
- >12-24 Weeks        86 <= onset day <= 169
- >24-36 Weeks        170 <= onset day <= 253
- >36 Weeks            onset day >= 254

Summaries will present the number of subjects reporting a TEAE by system organ class (SOC), preferred term, severity, relationship to study drug (causality), and seriousness. When summarizing TEAEs by severity and relationship, each subject will be counted once within a SOC or a preferred term by using the event with the greatest relationship or highest severity within each classification.

All information pertaining to an AE noted during the study will be listed by subject, detailing verbatim term given by the PI or designee, preferred term, SOC), onset date, resolution date, severity, seriousness, action taken, outcome and drug relatedness. The event onset will also be shown relative (in number of days) to date of first application.

Serious AEs (SAEs) will be summarized and listed using the same methodology as noted above. In addition, a listing of subjects who prematurely discontinued from the study due to an AE will be provided.

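### Protocol 9.4.5 makes no exception for mild or moderate visit-day skin reactions that lead to interruption, treatment or discontinuation; this conflicts with 9.4.10 and can leave such cases out of the AE outputs

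*Protocol*

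**What the plan says.** Protocol 9.4.5 scores five reactions on the face (burning/stinging, pruritus, erythema, dryness, peeling) from 0 to 3: "All subjects will be assessed for LSRs, on the face, at each visit". Two recording rules follow. For visit days: "LSRs observed on a visit day will not be recorded as adverse events unless scored as 3 (Severe"). For the time between visits: "Local skin reactions experienced by the subject in between study visits are to be recorded as an AE", with no grade threshold.

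Protocol 9.4.10 then ties changes in dosing to AEs: "Dose interruptions are allowed should a subject experience intolerable treatment-related adverse events (e.g., pruritis) on study". It also says "Study drug must be discontinued if an adverse event is deemed persistent", subject to the subject's interest. Protocol 10.3 gives a further reason to stop, "Unacceptable toxicity", without reference to an AE record.

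On outputs, SAP 6.8.2 tabulates AEs and adds that "a listing of subjects who prematurely discontinued from the study due to an AE will be provided". SAP 6.2 covers disposition: "The number of subjects enrolled, completed, and discontinued (including the reasons for discontinuation) will be summarized similarly". SAP 6.8.4.4 summarizes LSRs by visit, by worst post-baseline grade and by severity, and lists all of them. SAP 6.8.1 summarizes missed applications.

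**The concern.** AE status for a facial LSR depends only on when it is seen and how it is graded. What it led to plays no part. A mild reaction between visits is an AE, while a moderate one seen in clinic is not, even if dosing is interrupted or stopped because of it.

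Keeping routine visit-day LSRs out of the AE tables is a fair convention. The difficulty lies with reactions that have consequences. Action taken is collected for AEs (Protocol 9.4.7 and 11.4), whereas LSRs are recorded as grades. Protocol 9.4.10 assumes that a reaction such as pruritus prompting an interruption is an AE, but 9.4.5 read literally tells the site not to record it as one if it is grade 1 or 2 and seen on a visit day. With approximately 100 sites, the same event could be coded in different ways.

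The only stated objective is long-term safety and the analysis is descriptive, so correct classification of events is much of what the study delivers. Skin reactions have already been seen with this product: in the completed dose-ranging study, erythema was the most common LSR and application site pruritus was among the most common AEs (Protocol 1.2).

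**Working it through.** The plan gives no figure to reproduce. The check sets the rules side by side, follows cases through them, and adds two small calculations.

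**1. The recording rules (Protocol 9.4.5)**
- Visit day, grade 3: AE.
- Visit day, grade 1 or 2: not an AE; no exception for consequences.
- Between visits, any grade: AE.
- Present both at and between visits: not addressed.

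**2. Cases traced through the outputs**
- *Grade 2 pruritus felt at home and still present in clinic; dosing interrupted.* The between-visit rule makes it an AE and 9.4.10 expects one. The visit-day rule points the other way for the clinic observation. Most sites would probably record an AE, but the text leaves it open.
- *Grade 2 erythema graded by the investigator, not mentioned by the subject; dosing interrupted.* Under the visit-day rule there is no AE. The grade enters the LSR tables and listing. The interruption goes into the diary as a missed dose (9.4.10) and into the missed-application summary. Nothing connects the two.
- *Grade 2 dryness seen at an early termination visit before Day 22; the subject stops.* Under the visit-day rule there is no AE, so no entry in the AE-discontinuation listing. SAP 6.1.3 leaves early termination and unscheduled data before Day 22 out of the analyses, so the grade is only listed. The disposition table shows a reason for stopping, not the reaction.

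SAP 6.1.3 also drops early termination or unscheduled values when the mapped window already holds a scheduled visit. Those grades too would be only listed.

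**3. Share of days under the visit-day rule**
- Inputs: 9 clinic visits after Day 1 (Protocol 2); Week 36 target Day 253 (SAP 6.1.3).
- 9 / 253 = 3.6%.
- Subjects on active gel in the parent study: 9 + 3 = 12 analysis visits over 48 × 7 + 1 = 337 days; 12 / 337 = 3.6%.
- At Week 36 all drug is collected (Protocol 8.5), so an interruption could follow from at most 9 − 1 = 8 of the scheduled ACN05 clinic visits.

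A reaction strictly confined to a visit day is thus a narrow case. The share does not measure how often the problem arises, because visits are when LSRs are graded and compliance is reviewed.

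**4. Effect on compliance (SAP 6.8.1)**
- Expected = 2 × (duration − 2) + first-day doses + last-day doses − applications missed for a treatment-related AE.
- Assumptions: 253 days, one dose due on each of the first and last days, and a 2-day interruption (4 applications).
- Expected before any deduction: 2 × 251 + 1 + 1 = 504. Applied: 504 − 4 = 500.
- Not recorded as an AE: 500 / 504 = 99.2%.
- Recorded as a treatment-related AE: 500 / (504 − 4) = 100%.
- Difference: 0.8 percentage points, far from the 80% limit.

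**The case against.** A reader might infer that mild and moderate visit-day reactions are never AEs and that tolerability failures therefore disappear from the study's results. The documents do not support that.

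- Any LSR also experienced between visits is an AE at any grade. Dosing is twice daily at home and clinic visits are about four weeks apart, so a reaction bad enough to stop the gel will often have been felt before the visit or will continue after it.
- Protocol Table 2 makes the worst symptoms grade 3. Grade 2 pruritus does not disturb sleep and grade 2 burning is only somewhat bothersome. An intolerable itch or burn would usually be grade 3, and so an AE even on a visit day.
- All LSR grades are listed and most are tabulated. Discontinuation reasons and missed applications are summarized.
- 9.4.10 treats interruption for pruritus as a response to an AE. The protocol is therefore in conflict with itself; it does not clearly exclude these cases.
- The rule covers the face only. Reactions on the trunk in ACN03-origin subjects fall under the general AE definition in 9.4.6.

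All of this stands, and it narrows the point without removing it. The Table 2 argument is weaker for erythema, dryness and peeling, which the investigator grades, and for subjects who simply choose to stop. Open-ended AE questioning (9.4.6) may not bring out a sign that the subject does not think to mention. No planned output joins a reaction to the action it led to.

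**Conclusion.** The point holds in a limited form. Protocol 9.4.5 has no exception for grade 1 or 2 visit-day LSRs with consequences, is silent on reactions that span a visit, and does not fit 9.4.10. Following it literally can leave some cases out of the AE tables and the AE-discontinuation listing, most plausibly investigator-graded signs that the subject does not report between visits. They remain visible elsewhere, but without the link between reaction and action.

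The size cannot be estimated: the documents give no rate of grade 1 or 2 LSRs leading to interruption, treatment or withdrawal. The effect on compliance is negligible.

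The conclusion assumes that sites apply 9.4.5 as written and that the LSR form collects grades only, as the protocol describes; the form itself is not shown. The change is worth making because the study's sole objective is safety and the correction is cheap.

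**What to change.** Reconcile Protocol 9.4.5 with 9.4.10 by adding two recording statements to 9.4.5:

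1. An LSR of any grade, on any day, that leads to interruption or discontinuation of study drug, or to treatment, is also recorded as an AE with action taken.
2. An LSR present both at and between visits follows the between-visit rule.

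Other visit-day LSRs stay as they are. These statements govern recording only and alter no dosing or stopping rule.

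The cost is a short protocol change, a reminder to sites and slightly higher application-site AE counts. There is one side effect. SAP 6.8.2 pools AEs from ACN03 and ACN04 and tabulates them by 12-week period from the first active dose. If the parent studies record LSRs as 9.4.5 does now (their protocols are not among these documents), subjects who had active gel there would be under one rule up to Week 12 and another afterwards. A footnote to the 12-week-period tables should say so.

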**Table 2: Subject Assessed Local Skin Reactions**

Score	Grade	Burning/Stinging	Pruritus
0	None	No stinging/burning	No pruritus
1	Mild	Slightly warm, tingling sensation; not really bothersome	Occasional, slight itching/scratching
2	Moderate	Definite warm; tingling/stinging sensation that is somewhat bothersome	Intermittent itching/scratching which does not disturb sleep
3	Severe	Hot, tingling/stinging sensation that has caused definite discomfort	Bothersome itching/scratching which disturbs sleep

**Table 3: Investigator Assessed Local Skin Reactions**

Score	Grade	Erythema	Dryness	Peeling
0	None	None	None	None
1	Mild	Slight erythema: very light-pink	Perceptible dryness with no flakes or fissure formation	Mild diffuse peeling
2	Moderate	Dull red, clearly distinguishable	Easily noted dryness and flakes but no fissure formation	Moderate diffuse peeling
3	Severe	Deep/dark red	Easily noted dryness with flakes and fissure formation	Moderate to prominent, dense peeling

#### 9.4.6 Adverse Events

An adverse event (AE) is defined as any untoward medical occurrence associated with the use of a study drug in humans, whether or not considered drug related. An AE can, therefore, be any unfavorable and unintended sign (including an abnormal laboratory finding), symptom or disease temporally associated with the use of the study drug, whether or not related to the investigational product.

AEs will be monitored throughout the study. Subjects will be instructed to inform the Investigator and/or study staff of any AEs. At each visit, subjects will be asked about AEs in a non-specific manner using open-ended questions so as not to bias the response (e.g., How have you been since the last visit?). Specific inquiry regarding reported AEs will be conducted when applicable. All AEs will be documented and recorded in the subject's eCRF.

Any subject who has an AE (serious or non-serious) or clinically significant abnormal laboratory test value will be evaluated by the Investigator, and will be treated and/or followed up until the symptoms or values return to normal or to clinically acceptable levels, as judged by the Investigator. A physician, either at clinical site, or at a nearby hospital emergency room, will administer treatment for any serious adverse events (SAEs), if necessary. When appropriate, medical tests and examinations will be performed to document resolution of event(s).

### 9.4.7 Reporting

Only AEs that occur during or following study treatment with the drug will be reported in the AE section of the eCRF. Events recorded prior to treatment with the study drug will be reported in the Medical History section of the eCRF as appropriate. All AEs occurring during the course of the study will be individually recorded in the eCRF. A condition that is present prior to administration of study drug and that worsens after administration of study drug should be reported as an AE. Information regarding the onset, duration, severity, action taken, outcome, and relationship to study drug will be recorded.

New or worsening abnormal laboratory values and/or pulse and blood pressure are to be recorded as AEs if they are considered to be of clinical significance by the Investigator or meet the criteria of an SAE as described in [Section 9.4.8](#).

Unless a diagnosis is available, signs and symptoms must be reported as individual AEs in the eCRF; a diagnosis is preferred.

The severity of an AE will be designated as mild, moderate or severe. The term “severe” is used to describe the intensity of an adverse event; the event itself, however, may be of relatively minor clinical significance (e.g., ‘severe’ upper respiratory infection). Severity is not the same as “serious”. Seriousness of AEs is based on the outcome/action of an AE.

The relationship of the AE to the study treatment should be determined by the Investigator and will be based on the following two definitions:

**Not related:** An AE is defined as “not related” if the AE is not judged to be associated with the study drug and is attributable to another cause

**Related:** An AE is defined as “related” where a causal relationship between the event and the study drug is a reasonable possibility (possibly or probably related). A reasonable causal relationship is meant to convey that there are facts (e.g., evidence such as dechallenge/rechallenge) or other clinical arguments to suggest a causal relationship between the AE and study treatment.

